4.3.2 Dosage Modification

Dose modification of OCR is not permitted.

4.3.3 Overdose

There have been no observed overdoses in human clinical trials.

4.4 CONCOMITANT AND EXCLUDED THERAPY

All concomitant medications are allowed except immunosuppressants, lymphocyte-depleting agents, or lymphocyte-trafficking blockers while patients are receiving OCR. All medications including over-the-counter medication and supplements will be recorded at each clinical visit. At screening, all medications taken 4 weeks prior to screening will be reviewed and recorded, as well as all prior lifetime MS disease modifying therapies taken by the patient.

4.5 STUDY ASSESSMENTS

The investigator or designated research staff will obtain informed consent from each patient after explaining the purpose of the study and the potential risks and benefits known or can be reasonably expected. The IRB approved informed consent will be signed by the patient before any screening assessments or procedures are performed.

4.5.1 Assessments during Treatment

Visit 1/Screening Visit (-28 to -1 days prior to Baseline Day 0)

The following clinical and laboratory evaluations will occur within 28 days prior to Baseline (Day 0 OCR dose), unless otherwise noted. The investigator or designee must perform all screening evaluations to determine patient eligibility.

- Informed consent
- Eligibility review
- Demographic information
- Review of disease and medical history
- Review of prior and concomitant medications, including lifetime MS treatment history
- JC Virus Status and date of testing
- Reason(s) for switching to Ocrelizumab
- Vital signs
- Neurological exam (may be historical exam if completed within 28 days prior to consent)
- Relapse assessment (may be historical assessment if completed within 28 days prior to consent)
- Confirmation of estimated EDSS of 0 to 6, inclusive (If Screening is within 7 days prior to Baseline and a full EDSS was conducted at Screening, the EDSS is no longer required at the Baseline visit)
- Laboratory assessments:
 - CBC, CMP, and urine pregnancy test (female only) (may be historical laboratories if completed within 28 days prior to consent)
 - Hepatitis B testing (may be historical laboratories if completed within 6 months prior to consent)
- MRI (may be historical if completed within 6 weeks prior to Baseline (Day 0), recommended to be completed after last dose of NTZ. Must be completed prior first dose of OCR at Day 0)

Visit 2/Baseline Visit (Day -7 to Day 0)

The following clinical and laboratory evaluations will occur at baseline visit. The investigator or designee will review inclusion/exclusion criteria to confirm patient eligibility. Day 0 is defined as the day of OCR administration.

- Vital signs (not required if Baseline is within 7 days of Screening visit)

- Eligibility review
- Neurological exam (not required if Baseline is within 7 days of Screening visit)
- Relapse assessment (not required if Baseline is within 7 days of Screening visit)
- EDSS (not required if Baseline is within 7 days of Screening and a full EDSS was collected at Screening).
- MSIS-29 (if Baseline is within 7 days of Screening visit, may be collected at Screening instead of baseline visit).
- Laboratory assessments: CBC, CMP, Pregnancy test (female only) (not required if Baseline is within 7 days of Screening visit, but pregnancy test must be done if Screening Visit test was historical)
- Concomitant medications and adverse events (not required to be reviewed with the patient in person if Baseline is within 7 days of Screening visit, collect via chart review)
- OCR administration (300mg, 2 administrations: Day 0 and Day 14 ± 2 days)

Visit 3/3 Month Visit (Day 84 +/- 14 days from Baseline Day 0)

The following clinical and laboratory evaluations will occur 84 days from Baseline with a +/- 14 day window.

- Vital signs
- Neurological exam
- Relapse assessment
- EDSS
- Laboratory assessments: CBC, CMP, Pregnancy test (female only)
- MRI
- Concomitant medications and adverse events

Visit 4/6 Month Visit (Day 168 +/- 14 days from Baseline Day 0)

The following clinical and laboratory evaluations will occur 168 days from Baseline with a +/- 14 day window.

- Vital signs
- Neurological exam
- Relapse assessment
- EDSS
- MSIS-29
- Laboratory assessments: CBC, CMP, Pregnancy test (female only)
- MRI
- Concomitant medications and adverse events
- OCR administration (600mg)

Visit 5/9 Month Visit (Day 252 +/- 14 days from Baseline Day 0)

The following clinical and laboratory evaluations will occur 252 days from Baseline with a +/- 14 day window.

- Vital signs
- Neurological exam
- Relapse assessment
- EDSS
- Laboratory assessments: CBC, CMP, Pregnancy test (female only)
- Concomitant medications and adverse events

Visit 6/12 Month Visit (Day 336 +/- 14 days from Baseline Day 0)

The following clinical and laboratory evaluations will occur 336 days from Baseline with a +/- 14 day window.

- Vital signs
- Neurological exam
- Relapse assessment
- EDSS
- MSIS-29
- Laboratory assessments: CBC, CMP, Pregnancy test (female only)
- MRI
- Concomitant medications and adverse events
- OCR administration (600mg)

End of Study (EOS) Phone Contact (30 days +/- 14 days from study discontinuation)

The following clinical evaluation will occur 30 days +/- 14 days from study completion (12 Month OCR administration) or premature termination visit:

- Adverse events

Premature Termination Visit

If study drug is withdrawn and the patient is unwilling to continue in the trial for observation, complete a premature termination visit as soon as possible. If the patient discontinues from the study for any other reason noted in the subject discontinuation criteria, a premature termination visit must be performed as soon as possible. Patients who were withdrawn from the study for any reason will not be replaced. The following clinical and laboratory evaluations will be performed:

- Vital signs
- Neurological exam
- Relapse assessment
- EDSS
- MSIS-29
- Laboratory assessments: CBC, CMP, Pregnancy test (female only)
- Concomitant medications and adverse events
- Primary reason for discontinuation

Unscheduled Visits

Patients will be instructed to contact their treating physician in the event of a relapse and may be asked to return for unscheduled visit to assess any undesired clinical, or laboratory changes that occur during the study.

- Vital signs
- Neurological exam
- Relapse assessment
- EDSS
- Laboratory assessments: CBC, CMP, Pregnancy test (female only) (if indicated, per treating investigator)
- MRI (if indicated, per treating investigator)
- Concomitant medications and adverse events

Study Withdrawal

If a patient is lost to follow-up, she/he will be withdrawn from the study. Appropriate means of contact to consider lost to follow-up are 3 documented phone attempts and 1 certified letter.

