3. STUDY DESIGN

3.1 DESCRIPTION OF THE STUDY

This is a multicenter, prospective, open-label Phase IV clinical trial. Patients with relapsing forms of MS, ages 18 to 65, who have received a stable dose of NTZ for 12 or more consecutive months, and have been free of relapses, disability worsening or MRI progression 6 months prior to the transition screening visit will be eligible for the study. After informed consent to participate has been obtained, the patient will have a neurological exam, EDSS, 3T or 1.5T MRI, MSIS-29 and labs done for the screening visit to determine eligibility. 3T or 1.5T brain MRI with and without contrast will be performed with the standard MS protocol. It is preferred that the MRIs are done on a 3T scanner for this trial, but not required. MRIs will be performed with 3mm slice thickness with no gaps between slices. Patients will receive their first dose of OCR 4 to 6 weeks after the last dose of NTZ. Other baseline measures, including EDSS, MSIS-29, and labs will be performed within 4 weeks of screening. A neurological exam, EDSS, and labs will be performed at month 3, month 6, month 9, and month 12. MSIS-29 will be performed at months 6 and 12. MRIs will be performed at screening to determine

eligibility and at months 3, 6, and 12. All adverse events will be reported to the study sponsor. OCR will not be provided by the study; the medication will be supplied through the patient's commercial pharmacy and billed to the patient or the patient's insurance.

Patients will receive OCR 4-6 weeks after their last infusion of NTZ. OCR 300mg IV will be given on Day 0 and repeated with the same dose on Day 14±2. Patients will then receive OCR 600mg IV every 24 weeks.

If discontinuation of study drug occurs, the subject may continue in the trial for observational purposes. If willing to continue, they will complete all visit items moving forward, with the exception of study drug dosing and pregnancy testing (if applicable). If study drug is discontinued and the subject is unwilling to continue in the trial, a premature termination visit will be completed as soon as possible.

The target enrollment is 50 patients from 5 centers. Serious adverse events recorded during the trial will be reported to the study sponsor via Medwatch form.

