4.3.1 Dosage, Preparation, Administration and Storage

Ocrelizumab Formulation Packaging, and Handling

The following requirements are listed in the OCR prescribing information dated 11/2018 and are to be followed as part of the standard of care preparation of OCR for infusion. The study team is not responsible for collecting or reviewing data on how the drug was packaged, prepared, handled, or stored for the purposes of this trial.

Ocrelizumab will be supplied by the commercial pharmacy in a liquid formulation containing 30-mg/mL ocrelizumab in 20mM sodium acetate at pH 5.3, with 4% trehalose dihydrate and 0.02% polysorbate 20. The drug product is provided as a single-use liquid formulation in a 15-cc, type I USP, glass vial fitted with a 20-mm, fluoro-resin, laminated stopper and an aluminum seal with a flip-off plastic cap and contains a nominal 300 mg ocrelizumab. No preservative is used as each vial is designed for single use.

The ocrelizumab drug product must be diluted before administration. Solutions of ocrelizumab for IV administration are prepared by dilution of the drug product into an infusion bag containing 0.9% sodium chloride to a final drug concentration of 1 to 2 mg/mL.

Ocrelizumab may contain fine translucent and/or reflective particles associated with enhanced opalescence. Do not use the solution if discolored or if the solution contains discrete foreign particulate matter.

The infusion solution must be administered using an infusion set with an in-line, sterile, non-pyrogenic, low-protein-binding filter (pore size of up to 0.2 micrometer).

The prepared infusion solution of ocrelizumab is physically and chemically stable for 24 hours at 2–8°C and subsequently 8 hours at room temperature. The prepared infusion solution should be used immediately. If not used immediately, it can be stored up to 24 hours at 2–8°C. Infusion solution must be completely administered to the patient within 32 hours of preparation (not exceeding 24 hours at 2–8°C and 8 hours at room temperature). In the event an IV infusion cannot be completed the same day, the remaining solution should be discarded.

Dosage, Administration, and Compliance

Ocrelizumab 300mg IV will be given on Day 0 and repeated with the same dose on Day 14±2. Patients will then receive ocrelizumab 600mg IV every 24 weeks. Medication will not be provided by the study.

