5.2 METHODS AND TIMING FOR ASSESSING AND RECORDING SAFETY VARIABLES

The investigator is responsible for ensuring that all SAEs that are observed or reported during the study are collected and reported to the appropriate IRB(s) and Genentech, Inc. in accordance with CFR 312.32 (IND Safety Reports).

Adverse Event Reporting Period

The study period during which all AEs and SAEs must be reported begins after informed consent is obtained and ends 30 days following the last administration of study treatment or study discontinuation/termination, whichever is earlier. After this period, investigators should only report SAEs that are attributed to prior study treatment.

Assessment of Adverse Events

All AEs and SAEs whether volunteered by the subject, discovered by study personnel during questioning, or detected through examination, laboratory test, or other means will be reported appropriately. Each reported AE or SAE will be described by its duration (i.e., start and end dates), regulatory seriousness criteria if applicable, suspected relationship to ocrelizumab (see following guidance), and actions taken.

To ensure consistency of AE and SAE causality assessments, investigators should apply the following general guideline:

Yes

There is a plausible temporal relationship between the onset of the AE and administration of ocrelizumab, and the AE cannot be readily explained by the subject's clinical state, intercurrent illness, or concomitant therapies; and/or the AE follows a known pattern of response to ocrelizumab; and/or the AE abates or resolves upon discontinuation of ocrelizumab or dose reduction and, if applicable, reappears upon re-challenge.

No

Evidence exists that the AE has an etiology other than ocrelizumab (e.g., preexisting medical condition, underlying disease, intercurrent illness, or concomitant medication); and/or the AE has no plausible temporal relationship to ocrelizumab administration (e.g., event diagnosed 2 days after first dose of ocrelizumab).

Expected versus unexpected is to be evaluated for SAEs.

Expected adverse events are those adverse events that are listed or characterized in the prescribing information.

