APPENDIX A STUDY FLOWCHART

Procedure/Visit	Screening Visit #1 (Day -28 to -1)	Baseline Visit #2 (Day -7 to Day 0) ^W	Month 3 Visit #3 (Day 84 ±14)	Month 6 Visit #4 (Day 168 ±14)	Month 9 Visit #5 (Day 252 ±14)	Month 12 Visit #6 (Day 336 ±14)	EOS Phone Contact ^A	Premature Termination Visit ^B	UNS Visit ^C
Informed Consent	X								
Eligibility Review (INC/EXC)	X ^H	X ^I							
Disease and Medical History	X								
Demographics	X								
Reason(s) for switching to OCR	X								
Vital Signs ^S	X	X ^Y	X	X	X	X		X	X
Neuro Exam ^K	X ^U	X ^Y	X	X	X	X		X	X
Relapse Assessment	X ^U	X ^Y	X	X	X	X		X	X
EDSS	X ^T	X ^Y	X	X	X	X		X	X
MSIS-29 ^J		X ^Z		X		X		X	
Metabolic panel	X ^U	X* ^Y	X	X	X	X		X	X ^D
CBC ^Q	X ^U	X* ^Y	X	X	X	X		X	X ^D
Urine preg test ^E	X* ^U	X* ^Y	X*	X*	X*	X*		X*	X* ^D
JCV Antibody Status	X ^R								
Hepatitis B testing	X ^V								
MRI	X ^L		X*	X ^M		X ^M			X ^D
OCR Administration ^N		X ^F		X ^G		X ^G			
Primary Reason for Discontinuation								X	
Con meds	X ^O	X ^Y	X	X	X	X		X	X
Adverse Events		-----Monitor and record AEs at each visit after Screening-----							

*These items are paid for by the study.

A: 30 days ±7 days from study discontinuation (Month 12 OCR Administration or Premature Termination Visit).

B: If study drug is withdrawn and the patient is unwilling to continue in the trial for observation, complete a premature termination visit as soon as possible. If the patient discontinues from the study for any other reason noted in the subject discontinuation criteria, a premature termination visit must be performed as soon as possible.

C: Subjects will be instructed to contact their treating physician in the event of a relapse and may be asked to return for unscheduled visit to assess any undesired clinical, or laboratory changes that occur during the study.

D: To be performed only if indicated, per treating investigator.

E: For female subjects of childbearing potential only. If urine pregnancy test is positive, must be confirmed by serum pregnancy test. Not required at 2nd dose of 300mg OCR.

F: 300mg administered on Day 0, and then again on Day 14±2 days. First dose on Day 0 should be within 4 to 6 weeks of last dose of NTZ.

G: 600mg administration as one infusion.

H: At screening, review all eligibility criteria that are able to be assessed.

I: At baseline, eligibility must be reviewed prior to OCR administration to ensure all screening procedures/results are reviewed and subject meets all entrance criteria.

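### The end of adverse-event follow-up is set inconsistently: the final call has two windows, and the Section 5.2 reporting period closes while patients who have stopped ocrelizumab are still attending visits

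*Combined protocol and SAP*

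**What the plan says.** **The final call.** Section 4.5.1 plans one phone contact after the last visit, with AEs as its only item: "The following clinical evaluation will occur 30 days +/- 14 days from study completion (12 Month OCR administration) or premature termination visit". Footnote A of the Appendix A flowchart describes the same call as "30 days ±7 days from study discontinuation (Month 12 OCR Administration or Premature Termination Visit").

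**The reporting period.** Under Section 5.2 the period for AEs and serious AEs (SAEs) opens at consent and "ends 30 days following the last administration of study treatment or study discontinuation/termination, whichever is earlier". The next sentence reads: "After this period, investigators should only report SAEs that are attributed to prior study treatment".

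**Patients who stop ocrelizumab but stay.** Section 3.1 allows this: "If willing to continue, they will complete all visit items moving forward, with the exception of study drug dosing and pregnancy testing". AEs are on the Section 4.5.1 lists for the Month 3, 6, 9 and 12 visits, and the flowchart says "Monitor and record AEs at each visit after Screening". The opening of Section 5 asks for every AE to go on the case report form, whatever its severity or relationship to the drug. Section 4.9.4 promises AE summaries for all patients.

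**Patients who leave.** The premature termination visit is for those who do not remain under observation: "If study drug is withdrawn and the patient is unwilling to continue in the trial for observation, complete a premature termination visit". Section 4.5.1 also requires it for patients who leave the study for other reasons.

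**Dosing calendar.** Infusions are on Day 0 and Day 14±2; "Patients will then receive ocrelizumab 600mg IV every 24 weeks", which the visit schedule places at Day 168 and Day 336.

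**The concern.** These passages do not give one end date for AE follow-up. The two call windows cannot both apply. The 5.2 rule also works against the visit schedule for one group. A patient who stops ocrelizumab and stays has a last infusion that precedes study discontinuation, so the earlier-of-two rule closes the reporting period 30 days after that infusion. The same patient goes on attending visits at which AEs are to be collected.

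AEs and SAEs are a secondary outcome (3.3.2), infections during the trial are an ancillary outcome (3.3.3), and tolerability is a secondary objective (2.2). A site that follows 5.2 would leave out new non-serious AEs, and SAEs not attributed to treatment, that start after the close. A site that follows the visit schedule would record them. Section 5.3 ties the reporting of deaths regardless of cause to the same period. With 50 patients at 5 centres, the AE summaries would then have no single at-risk period for those who stopped treatment.

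**Working it through.** The plan gives no figure to reproduce here. The check is day arithmetic on its own dates.

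**1. The call window.** Days are counted from the anchor.
- Section 4.5.1: 30 − 14 = 16 to 30 + 14 = 44, which is 29 possible days.
- Appendix A: 30 − 7 = 23 to 30 + 7 = 37, which is 15 possible days.
- Allowed by 4.5.1 but not by Appendix A: days 16–22 (7 days) and 38–44 (7 days), so 14 of 29.
- For a patient infused on Day 336, the call falls on Day 352–380 under 4.5.1 and on Day 359–373 under Appendix A.

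**2. The reporting period for a patient who stops and stays.** Close of period = day of last infusion + 30. Days outside = 336 − close.

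| Last infusion | 5.2 period closes | Scheduled AE visits after the close | Days outside, of 336 |
|---|---|---|---|
| Day 0 | Day 30 | Days 84, 168, 252, 336 | 306 (91%) |
| Day 14 | Day 44 | Days 84, 168, 252, 336 | 292 (87%) |
| Day 168 | Day 198 | Days 252, 336 | 138 (41%) |

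The permitted windows do not change this. A second infusion on Day 12–16 gives a close on Day 42–46, and the earliest Month 3 visit is Day 84 − 14 = 70. A Month 6 infusion on Day 154–182 gives a close on Day 184–212, and the earliest Month 9 visit is Day 252 − 14 = 238.

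**3. A different parse of 5.2.** Suppose the 30 days attach only to the last infusion, and study discontinuation closes the period at once. For a patient still under observation the infusion limb still comes first, so the table stands.

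**4. What remains reportable after the close.** SAEs attributed to ocrelizumab stay reportable (5.2, and 5.3 item g). Clinically significant AEs of moderate or higher severity that are already known are followed to resolution or stabilization, beyond the final call (Section 5). What 5.2 excludes is new non-serious AEs and SAEs not attributed to treatment.

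**5. The call's anchor.** Both passages name two events in parentheses: the Month 12 infusion or the premature termination visit. A patient who stops ocrelizumab and completes observation has neither.

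**The case against.** The strongest reply is that nothing need be lost. Section 5 requires all AEs to be recorded, the visit lists collect them, and 5.2 can be read as governing onward reporting to the IRB and the manufacturer. No passage tells a site to remove an AE already entered. Patients also hold study telephone numbers for reporting AEs. Much of this stands, and many sites would probably keep recording. It does not settle the matter, because the title of 5.2 covers recording as well as assessment, and its period applies to all AEs. The wording is ambiguous, and sites can differ in good faith.

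A second reply is that the call's anchor can be inferred, since the 4.5.1 heading refers to study discontinuation and its text to study completion. That is fair. The defect is that the parenthetical events do not fit this group, not that no date can be guessed.

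Two stronger readings are tempting, and the documents do not support either.

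- A reader might infer that the AEs which cause patients to stop are the ones most likely to be lost. When such an event arises, nobody yet knows that the previous infusion was the last, so it would be recorded in the ordinary way. Infusion reactions, a named reason for stopping, fall close to an infusion and so within the 30 days. Serious events attributed to ocrelizumab stay reportable at any time. The reason for and date of discontinuation are collected separately (4.5.1 and 4.9.1).
- A reader might object that the call can take place before day 30. A symmetric window around a 30-day call is ordinary scheduling tolerance. The fault is that two different windows are stated.

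**Conclusion.** The inconsistency is real and minor. The call windows conflict outright, on 14 of 29 days. For a patient who stops after Day 14 or Day 168 and stays, the 5.2 period leaves out 292 or 138 of the 336 days over which the visit schedule still collects AEs. These counts use nominal infusion and visit days and the literal earlier-of-two rule.

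The trial-wide effect cannot be quantified. A reader might try to scale the table by the pivotal-trial withdrawal rates in 3.2 (3.2% and 3.8%) or the 10% attrition allowance in 4.9.6. Neither counts patients who stop ocrelizumab and remain under observation, and the documents give no such number. The primary endpoint, the proportion relapse-free at month 12, does not depend on any of these passages.

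**What to change.** Reconcile Sections 3.1, 4.5.1 and 5.2 with Appendix A:

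- State one call window, the same in 4.5.1 and in footnote A. Which one is for the sponsor to choose.
- Amend the end-of-period rule in 5.2 so that it does not close while a patient is still attending protocol visits at which AEs are collected.
- For patients who stop ocrelizumab and complete observation, anchor the call to the last study visit.
- In the safety analysis, include every AE recorded at a protocol visit, and flag those that start more than 30 days after the last infusion so that they can also be shown separately.

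The cost is wording changes in those places and one flag in the AE listing. No visit is added, because AEs are already an item at each scheduled visit.

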3.3 OUTCOME MEASURES

3.3.1 Primary Outcome Measure

The primary endpoint is the proportion of relapse-free patients at month 12 after switching from NTZ to OCR.

Relapse is defined as:

Protocol: Ocrelizumab Providence Health & Services

Page 5 of 34 ML39655

- Occurrence of new or worsening neurological symptoms attributable to MS
- Symptoms persisting for > 24 hours
- Symptoms not attributable to confounding clinical factors (e.g., fever, infection, injury, adverse reaction to medication)
- Symptoms immediately preceded by a stable or improving neurological state for at least 30 days
- Symptoms accompanied by objective neurological worsening consistent with an increase of at least half a step on the EDSS scale, or 2 points on one of the appropriate FSS, or 1 point on 2 or more of the appropriate FSS; the change has to affect the selected FSS (i.e. pyramidal, ambulation, cerebellar, brainstem, sensory, or visual)

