3.4 SAFETY PLAN

Patients will be evaluated at each study visit for the duration of their participation in the study (see Section 4.5 and Appendix A, Study Flowchart).

Protocol: Ocrelizumab Providence Health & Services

Page 6 of 34 ML39655

A full neurologic examination will be conducted at every visit (may be historical at screening if an exam was completed within 28 days prior to consent, and may be waived at baseline if screening and baseline are 7 or less days apart). Any worsening or new abnormality (including laboratory results) that is determined by the investigator as clinically significant will be recorded as an AE and will be monitored until resolution or stabilization. MS related symptoms are not to be reported as AEs unless, in the opinion of the investigator, the symptoms are unusually serious and relevant.

The recommendation from the OCR prescribing information dated 11/2018 is to pre-medicate with 100mg of methylprednisolone (or an equivalent corticosteroid) administered intravenously approximately 30 minutes prior to each OCR infusion to reduce the frequency and severity of infusion related reactions (IRRs) [see Warnings and Precautions (5.1) in prescribing information]. Also, it is recommended to pre-medicate with an antihistamine (e.g., diphenhydramine) approximately 30-60 minutes prior to each OCR infusion to further reduce the frequency and severity of infusion reactions.

Recommended medications to be available if there is an infusion reaction (per treating investigator discretion):

- A. Epinephrine – anaphylaxis
- B. Albuterol – bronchospasm or hypoxia
- C. Famotidine 20mg IV – hives, itching, or anaphylaxis
- D. Oxygen therapy – shortness of breath, chest pain, or hypoxia
- E. Acetaminophen – pain, fever, and headaches
- F. Methylprednisolone – hives, itching, shortness of breath, or anaphylaxis

Patients administered a sedating antihistamine for the treatment or prevention of IRRs should be given appropriate warnings concerning drowsiness and potential impairment of ability to drive or operate machinery.

Pre-medications, infusion reaction management, and infusion reaction medications are to be left to treating investigator discretion.

Suggested Management of IRRs

Severe IRRs

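### A relapse needs objective EDSS/FSS worsening, but the visit that would document it is optional and untimed, so some relapses may go uncounted and the relapse-free proportion can only be pushed upward

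*Combined protocol and SAP*

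**What the plan says.** Section 3.3.1 sets the endpoint: "The primary endpoint is the proportion of relapse-free patients at month 12 after switching from NTZ to OCR". Its relapse definition lists several conditions. One is duration: "Symptoms persisting for > 24 hours". Another is the objective one: "Symptoms accompanied by objective neurological worsening consistent with an increase of at least half a step on the EDSS scale", with stated changes on the functional system scores as alternatives.

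Section 4.5.1, under Unscheduled Visits, gives the route by which a relapse between visits reaches the study: "Patients will be instructed to contact their treating physician in the event of a relapse". It then says that the patient "may be asked to return for unscheduled visit to assess any undesired clinical, or laboratory changes that occur during the study". Footnote C of the Appendix A flowchart repeats the rule: "Subjects will be instructed to contact their treating physician in the event of a relapse and may be asked to return for unscheduled visit". Neither place makes the visit obligatory or sets a time limit. If the visit takes place, neurological exam, relapse assessment and EDSS are all part of it.

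Scheduled EDSS examinations after baseline fall at Days 84, 168, 252 and 336, each with a window of 14 days either way. For month 3, for example: "The following clinical and laboratory evaluations will occur 84 days from Baseline with a +/- 14 day window".

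Adverse event reporting is not a dependable second route, because Section 3.4 says: "MS related symptoms are not to be reported as AEs unless, in the opinion of the investigator, the symptoms are unusually serious and relevant".

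**The concern.** The definition asks for a finding that has to be observed while the deficit is present, and the plan leaves that observation to discretion. Symptoms need to last only just over a day, so a short relapse qualifies if someone examines the patient in time. If nobody does, a history taken at the next quarterly visit cannot supply a change in score that has already resolved.

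Section 4.9.5 covers discontinuation and missed interim visits but has no rule for a relapse that was reported and not examined. Without one, the natural result is that the patient stays event-free in the Kaplan-Meier analysis.

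The direction of this error is fixed: a missed examination can remove a relapse but cannot create one. It would raise the relapse-free proportion, lower the ARR and lengthen the time to first relapse. There is no control arm to share the under-count, the result is read as an absolute proportion, and the decision on whom to call in rests with unblinded staff.

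**Working it through.** **Inputs.** From Section 4.9.6: assumed relapse-free proportion 0.80, lower limit 0.68 with 95% confidence, 45 evaluable patients, 10% attrition, 50 in total. From Section 4.9.3: two-sided intervals at the 0.05 level. From Section 4.5.1: visits 84 days apart, each ±14 days. The share of relapsing patients missed, m, is not in the documents. It is an assumption, varied here from 10% to 30%.

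**1. The plan's own figure.** The two-sided normal-approximation limit, without censoring, is 0.80 − 1.96 × √(0.80 × 0.20 / 45) = 0.80 − 0.117 = 0.683. For a half-width of exactly 0.12, n = 1.96² × 0.16 / 0.12² = 42.7, so 43, close to the stated 45. For attrition, 45 / 0.90 = 50. The sample size reproduces and is not at fault.

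**2. Gap between examinations.** Two consecutive post-baseline visits can each move by 14 days, so the gap runs from 84 − 28 = 56 days to 84 + 28 = 112 days.

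**3. Effect on the primary endpoint.** Let m be the share of relapsing patients for whom no relapse is counted. Then observed = 1 − (1 − true) × (1 − m).

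| m (assumed) | true 0.80 reads | true 0.90 reads |
|---|---|---|
| 10% | 1 − 0.20 × 0.90 = 0.82 | 1 − 0.10 × 0.90 = 0.91 |
| 20% | 1 − 0.20 × 0.80 = 0.84 | 1 − 0.10 × 0.80 = 0.92 |
| 30% | 1 − 0.20 × 0.70 = 0.86 | 1 − 0.10 × 0.70 = 0.93 |

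**4. Read backwards.** With true = 1 − 0.20 / (1 − m), an observed 0.80 would correspond to a true 0.778, 0.750 or 0.714 at the same three values of m.

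**5. ARR.** Follow-up time is unchanged when a relapse is not counted. If a share r of all relapses is missed, the observed ARR is (1 − r) times the true one. The share r need not equal m: a patient with two relapses is misclassified at month 12 only if both are missed, but loses from the ARR with each one missed.

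**The case against.** The strongest reply is that the gap is narrower than it first looks.

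- Neurological exam, relapse assessment and EDSS are done at every visit from month 3 to month 12 and at premature termination, so a residual deficit can still be found.
- The definition does not say that the objective evidence must come from a study visit. Patients are told to call their treating physician and ocrelizumab is given as standard care, so an examination in routine practice is not excluded.
- Sites may call patients in anyway.
- Medications are recorded at each clinical visit (Section 4.4), so a relapse treated between visits should leave a trace.

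All of this stands, and it limits the point to relapses that are examined nowhere and leave no measurable deficit at the next visit. It does not close the gap. A medication record does not supply an EDSS/FSS change, the content of the relapse assessment is not described, and no section requires a timed examination.

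Two stronger readings are tempting. A reader might infer that any relapse recovering between quarterly visits is bound to be scored relapse-free. The documents do not say so: they give no scoring rule for a reported but unexamined relapse, and the loss is a risk, not a certainty. A reader might also set the six-point shift at m = 30% against the 0.12 between 0.80 and 0.68 and call it half of a margin. Section 4.9.6 gives 0.68 as the lower confidence limit to be reached if the proportion is 0.80. That is a statement of precision; the plan names no non-inferiority margin, so the comparison carries no decision meaning.

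**Conclusion.** The concern holds as a risk of one-directional under-counting. The objective criterion and the optional, untimed visit are both in the current text, and nothing else in the plan guarantees the examination. The relapses at risk are those not examined anywhere and with no deficit left at the next scheduled visit, which may be up to 112 days after the one before.

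The size is unknown. Under the assumed 10% to 30% of relapsing patients missed, the bias is 2 to 6 percentage points if the truth is 0.80 and 1 to 3 points if it is 0.90. The documents support no particular value of m. The sample size of 45 evaluable and 50 enrolled is unaffected. The change is worth making because the direction is known, there is no comparison group to offset it, and the repair is cheap.

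**What to change.** 1. **Make the visit required and timed.** In Section 4.5.1 (Unscheduled Visits) and in footnote C of Appendix A, replace the optional wording with an obligation: *a patient who reports a suspected relapse will be asked to return for an unscheduled visit with neurological exam and EDSS/FSS within a stated number of days of the report*. Seven days is one example; the window is for the sponsor to choose.
2. **Log every report.** Record each patient-reported suspected relapse with its onset date and whether and when it was examined.
3. **Add a sensitivity analysis** of the primary endpoint and the ARR that counts suspected relapses not examined in the window as events, unless they fail the other criteria of Section 3.3.1 (duration, confounding factors, 30 days of prior stability). Label it a worst-case bound, since some of these episodes will not be true relapses.

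**Cost.** At the planning value about 50 × 0.20 = 10 patients would relapse. Suspected relapses that prove not to be relapses add visits, in a number that the documents do not allow one to estimate. The visit type already exists with the needed assessments. Its funding must be settled, because Appendix A does not mark the unscheduled exam and EDSS as paid for by the study. The log and the sensitivity analysis need no extra visit, and the sample size does not change.
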